2.6 Summary of Antibiotics and Other Medications

Descriptive summaries of antibiotics received by participants are presented by treatment duration arm within ERR and NERR groups. Also summarized is the use of steroids or airway clearance any time during the study. Proportion of patients retreated with IV antibiotics (as collected in the CFFNPR) for pulmonary exacerbation within 30 days following scheduled completion of IV antibiotic treatment is summarized by treatment duration arm within ERR and NERR groups and differences in the proportion of subjects are estimated and tested using a two-sided test of proportions.

2.7 Time to Next Pulmonary Exacerbation

Time (days) to next exacerbation following scheduled completion of IV antibiotics is presented using Kaplan-Meier survival estimation and compared between treatment durations within ERR and NERR groups using a Cox proportional hazards model with a test of the treatment effect at a two-sided significance level of 0.05. The hazard ratio and its 95% confidence interval are presented. Additionally, results from a model adjusted for randomization strata are shown. Also performed are exploratory analyses testing proportion of time spent receiving home IVs and the timing of corticosteroid initiation.

2.8 Summary of CRISS

Absolute change in CRISS from Baseline (Visit 1) to two weeks after scheduled completion of IV antibiotics (Visit 3) is summarized. Mean differences between treatment duration arms within ERR and NERR groups at each visit and corresponding 95% CIs are presented. Changes from Baseline (Visit 1) to Visit 3 are assessed using a two-sample, two-sided t-test. Additionally, an ANOVA model adjusted for randomization strata is used to compare the change in CRISS between treatment duration arms within ERR and NERR groups. Also summarized is the proportion of participants who experienced a clinically meaningful reduction in CRISS of 11 or more units.

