Descriptive summaries of antibiotics received by patients will be presented by treatment duration arm within ERR and NERR groups. Proportion of patients retreated with IV antibiotics (as collected in the CFFNPR) for pulmonary exacerbation within 30 days following scheduled completion of IV antibiotic treatment will be summarized by treatment duration arm within ERR and NERR groups and differences in the proportion of subjects will be estimated and tested using a two-sided test of proportions. Time (days) to next exacerbation following scheduled completion of IV antibiotics will be presented using Kaplan-Meier survival estimation and compared between treatment durations within ERR and NERR groups using a Cox proportional hazards model with a test of the treatment effect at a two-sided significance level of 0.05. The hazard ratio and its 95% confidence interval will be presented. An additional secondary analysis may stratify by or adjust for the randomization strata.

Absolute change in CRISS, relative change in FEV₁ (liters), and absolute change in weight (kg) from Baseline (Visit 1) to two weeks after scheduled completion of IV antibiotics (Visit 3) will be summarized. Mean differences between treatment duration arms within ERR and NERR groups at each visit and corresponding 95% CIs will be presented. Changes from Baseline (Visit 1) to Visit 3 will be assessed using a two-sample, two-sided t-test and additional secondary analysis may adjust for the randomization strata.

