2.9 Summary of Spirometry Results

Absolute and relative changes in spirometry measures from Baseline (Visit 1) to each post-baseline visit are summarized. Mean differences between treatment duration arms within ERR and NERR groups at each visit and corresponding 95% CIs are presented. Changes from Baseline (Visit 1) to Visit 3 are assessed using a two-sample, two-sided t-test. Additionally, an ANOVA model adjusted for randomization strata is used to compare the relative change in FEV₁ (L) between treatment duration arms within ERR and NERR groups.

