2.10 Summary of Anthropometric Measures

Absolute changes in weight (kg) and BMI from Baseline (Visit 1) to each post-baseline visit are summarized. Mean differences between treatment duration arms within ERR and NERR groups at each visit and corresponding 95% CIs are presented. Changes from Baseline (Visit 1) to Visit 3 are assessed using a two-sample, two-sided t-test. Additionally, an ANOVA model adjusted for randomization strata is used to compare the change in weight (kg) between treatment duration arms within ERR and NERR groups.

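### The first-stated tests of the secondary endpoints use neither the strata nor the baseline value as covariates: valid, but imprecise, and 30-day retreatment has no adjusted analysis

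*SAP*

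**What the plan says.** Protocol 8.1 stratifies randomisation within each response group on four two-level factors: Visit 1 FEV1, IV-treated exacerbations in the prior year, treatment location by Visit 2, and systemic corticosteroid use by Visit 2. SAP 2.5 gives the primary endpoint one model, an ANOVA adjusted for all four.

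The secondary endpoints are handled as follows.

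- **CRISS, relative FEV1 (L), weight (SAP 2.8 to 2.10).** The first-stated test is unadjusted: "Changes from Baseline (Visit 1) to Visit 3 are assessed using a two-sample, two-sided t-test". A second analysis follows. For CRISS: "Additionally, an ANOVA model adjusted for randomization strata is used to compare the change in CRISS". For weight: "an ANOVA model adjusted for randomization strata is used to compare the change in weight (kg) between treatment duration arms". SAP 2.9 does the same for relative change in FEV1.
- **Time to next exacerbation (SAP 2.7).** An unadjusted Cox model is tested at 0.05, and then: "Additionally, results from a model adjusted for randomization strata are shown".
- **30-day retreatment (SAP 2.6).** There is one analysis only: "differences in the proportion of subjects are estimated and tested using a two-sided test of proportions".

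Protocol 15.4 makes adjustment optional for the three continuous endpoints: "additional secondary analysis may adjust for the randomization strata". The SAP makes it definite but does not state which result leads. No secondary model has the endpoint's own Visit 1 value as a covariate.

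**The concern.** When randomisation is stratified on factors that predict the outcome, the arms are balanced on them by design. A two-sample t-test does not take credit for that balance. Its standard error is too large and its true error rate falls below the nominal 5%. Separately, a change score tends to correlate negatively with its starting value, so leaving baseline out of the model leaves explainable variance in the residual. Baseline CRISS and baseline weight are not strata, so the planned ANOVA contains nothing in their place.

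Retreatment is the clearest gap. Prior-year exacerbation count is a natural predictor of early retreatment and was judged important enough to stratify on, yet the analysis does not use it.

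The cost is precision. In the ERR group, where the shorter course is meant to be no worse, an unnecessarily wide interval makes a real worsening in symptoms or retreatment harder to see. A smaller issue is that four of the five secondary efficacy endpoints will have two results with no explicit statement of which one leads.

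**Working it through.** **1. The plan's own figures.** Protocol 15.7 gives power and precision for the primary endpoint only. With SD 9 and two-sided alpha 0.05:

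- ERR, 155 per arm, margin 3.5: SE = 9·√(2/155) = 1.022. Power = Φ(3.5/1.022 − 1.96) = 92.8% (stated 93%). Half-width = 1.96 × 1.022 = 2.00 (stated 2%).
- NERR, 285 per arm, difference 2.5: SE = 9·√(2/285) = 0.754. Power = Φ(2.5/0.754 − 1.96) = 91.2% (stated 91%). Half-width = 1.48 (stated 1.5%).

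These reproduce. No power or precision is stated for any secondary endpoint, so the effects below are relative, and ρ and R² are assumptions.

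**2. Adding the baseline value to a difference score.** Let ρ be the correlation between Visit 1 and Visit 3, with equal SDs at both visits. The variance ratio of ANCOVA to the change-score test is (1 + ρ)/2. The interval narrows by 1 − √((1 + ρ)/2). A comparison with 80% power moves to Φ((1.96 + 0.84)/√((1 + ρ)/2) − 1.96).

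| ρ (assumed) | Variance ratio | CI narrower by | 80% power becomes |
|---|---|---|---|
| 0.4 | 0.70 | 16.3% | 91.8% |
| 0.5 | 0.75 | 13.4% | 89.9% |
| 0.7 | 0.85 | 7.8% | 86.0% |
| 0.9 | 0.95 | 2.5% | 82.0% |
| 0.95 | 0.975 | 1.3% | 81.0% |

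The upper rows are plausible for a symptom score such as CRISS. The last two are likely for adult weight over 24 to 35 days. Relative change in FEV1 divides by baseline, so it is not a difference score and this formula does not apply to it directly.

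**3. Using the strata.** If the strata explain a fraction R² of outcome variance, adjustment narrows the interval by 1 − √(1 − R²). The true two-sided alpha of the unadjusted t-test under stratified randomisation is about 2·(1 − Φ(1.96/√(1 − R²))).

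| R² (assumed) | CI narrower by | True alpha of t-test |
|---|---|---|
| 0.02 | 1.0% | 0.048 |
| 0.05 | 2.5% | 0.044 |
| 0.10 | 5.1% | 0.039 |
| 0.20 | 10.6% | 0.028 |

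For the three continuous endpoints this gain is already available from the additional ANOVA.

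**4. Two results side by side.** Trials with 155 and 285 per arm were simulated with four binary strata, assumed prevalences, blocks of four within the 16 cells, and R² from 0.05 to 0.20. There were 6,000 null and 3,000 alternative replicates per setting.

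- Under the null, the chance that at least one of the t-test and the strata-adjusted ANOVA is significant was 4.6% to 5.4%. That is 5% within simulation error.
- The two tests fell on opposite sides of 0.05 in about 0.5% to 2.3% of null trials, and in about 2% to 11% of trials where the t-test had roughly 50% power.

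**5. Retreatment.** The documents give neither a retreatment rate nor its association with the strata, so no size can be attached. Four two-level factors make 2⁴ = 16 combinations. With 310 ERR completers that averages 310/16 ≈ 19 per combination across both arms, so a fully stratified estimator could meet sparse cells.

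**The case against.** Several stronger readings are tempting, and the documents do not support them.

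- *A reader might infer that the plan throws the strata away.* It does not. Strata-adjusted models are planned for CRISS, relative FEV1, weight and time to next exacerbation. Only retreatment lacks one.
- *A reader might infer that baseline is ignored.* The three continuous endpoints are changes from Visit 1, so baseline enters through the outcome. Visit 1 FEV1, split at 50% predicted, is also a term in the planned ANOVA. What is missing is the extra ANCOVA precision.
- *A reader might infer that two p-values per endpoint let the trial pick a false positive.* Step 4 shows no material inflation, because the t-test is itself conservative, and retreatment has only one test. The words chosen in both documents also imply that adjustment is supplementary; the order is implicit, not absent.
- *A reader might apply the 8% to 16% gain to every endpoint.* It depends on low to moderate correlation. As an illustration, take the planning SD of 9 for absolute FEV1 change and assume a between-subject SD of 20. Then ρ = 1 − 81/(2 × 400) ≈ 0.90, where the gain is about 2.5%.

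It is also fair to say that these are secondary endpoints, that Protocol 15.4 frames their analysis as largely descriptive, and that a valid but conservative test is not an error. Finally, an adjusted Cox hazard ratio is conditional and non-collapsible. Promoting it changes what is estimated, so it is not a pure precision gain. All of this stands and limits the severity. It does not remove the case for using covariates already in hand, or for adjusting the retreatment comparison.

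**Conclusion.** The point holds as a matter of efficiency. The first-stated tests for CRISS, relative FEV1 and weight, and the only test for 30-day retreatment, are valid but less precise than the design allows. Assuming equal SDs, the gain from adding baseline is about 16% to 8% of interval width at correlations of 0.4 to 0.7, and 2.5% to 1.3% at 0.9 to 0.95. It is therefore worthwhile mainly for CRISS, small for weight, and not quantified here for relative FEV1. The strata contribute a further gain that depends on an unknown R² and, outside retreatment, is already planned as a second analysis. Which analysis leads can alter a borderline secondary result, but error control is not at stake. Severity is minor.

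**What to change.** - **SAP 2.8 to 2.10:** name a single inferential analysis for each endpoint, an ANCOVA of change on treatment arm, the four strata and that endpoint's Visit 1 value. Label the t-test supportive.
- **SAP 2.6:** replace the crude test with a strata-adjusted risk difference and its 95% CI. Obtain it from a main-effects logistic model with standardisation, which avoids sparse cells among the 16 strata combinations.
- **SAP 2.7:** the strata-adjusted Cox model is already planned, so only state which Cox result leads.

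The strata and Visit 1 values are already collected. The cost is SAP wording and a few lines of code, with no extra patients or visits, provided the change is made before the SAP is finalised.

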2.9 Summary of Spirometry Results

Absolute and relative changes in spirometry measures from Baseline (Visit 1) to each post-baseline visit are summarized. Mean differences between treatment duration arms within ERR and NERR groups at each visit and corresponding 95% CIs are presented. Changes from Baseline (Visit 1) to Visit 3 are assessed using a two-sample, two-sided t-test. Additionally, an ANOVA model adjusted for randomization strata is used to compare the relative change in FEV₁ (L) between treatment duration arms within ERR and NERR groups.

2.10 Summary of Anthropometric Measures

Absolute changes in weight (kg) and BMI from Baseline (Visit 1) to each post-baseline visit are summarized. Mean differences between treatment duration arms within ERR and NERR groups at each visit and corresponding 95% CIs are presented. Changes from Baseline (Visit 1) to Visit 3 are assessed using a two-sample, two-sided t-test. Additionally, an ANOVA model adjusted for randomization strata is used to compare the change in weight (kg) between treatment duration arms within ERR and NERR groups.

2.11 Summary of CRP Results

Clinical lab CRP at each of the study visits and change in CRP from Baseline (Visit 1) are summarized by response group (ERR and NERR) and by treatment duration arm. Associations between Baseline (Visit 1) CRP and change in CRP with clinical outcomes (e.g. baseline values and changes in spirometry, weight, and CRISS) are summarized. Further, clinical baseline characteristics and outcomes are summarized by CRP response.

2.12 Randomized Completers, Randomized Lost to Follow-up, and Un-Randomized Participants

Baseline characteristics of the un-randomized subjects are summarized descriptively. Similarly, the randomized but lost to follow-up subjects (no Visit 3) are described. Comparisons of these two groups with the randomized completed subjects are performed for baseline characteristics, treatments and outcomes utilizing both the study data and the CFFNPR.

2.13 ERR-14 and NERR-14 Participants

Descriptive comparisons of the two cohorts treated for 14 days (ERR-14 and NERR-14) are performed to characterize associations between early assessments of clinical response (at Visit 2) and after completion of treatment for a PEx (Visit 3). Comparisons of these two groups are performed for baseline characteristics, treatments and outcomes utilizing both the study data and the CFFNPR.

2.14 Study Impact on PEx Treatment Duration

Summarized are distributions of pulmonary exacerbation treatment durations (as collected in the CFFNPR) observed at the STOP2 study centers during the conduct of this study and after the study completion (Month, Year through Month, Year). Also shown are distributions of pulmonary treatment durations observed at a select non-STOP2 CF centers during the same time frames.

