8 STUDY TREATMENTS

8.1 Method of Assigning Subjects to Response Group and Treatment Arms

All eligible subjects will undergo pulmonary function testing (spirometry) and complete a respiratory symptom score (CRISS) at Baseline (Visit 1) and at Day 7-10 (Visit 2). At Visit 2, subjects will be allocated to either the ERR or NERR group based upon their initial clinical response as determined by the change from Baseline in FEV₁ (percent of predicted as determined by GLI equations)^{18,19} and CRISS and then randomized to a treatment arm (duration nested within response group). The spirometry and CRISS measures must be present and entered into EDC for both Baseline (Visit 1) and Visit 2 for randomization to occur.

ERR subjects [$\geq 8\%$ predicted improvement in FEV₁ from Baseline (Visit 1) to Visit 2 and CRISS reduction of ≥ 11 points from Baseline (Visit 1) to Visit 2] will be randomized 1:1 to either 10 days (ERR-10) or 14 days (ERR-14) total IV antibiotic treatment duration while remaining subjects not meeting the ERR threshold will be randomized 1:1 to receive either 14 (NERR-14) or 21 (NERR-21) days total IV antibiotic treatment duration. A minimum of 310 subjects (155 per duration arm) will be allocated to the ERR group and a minimum of 570 subjects (285 per duration arm) to the NERR group. Randomization will occur by a predetermined scheme. Within each response group, subjects will be stratified by Visit 1 FEV₁ (FEV₁ < 50% of predicted versus $\geq 50\%$ predicted), number of IV-treated exacerbations in prior year (0-1 versus 2+ in prior year), location of IV treatment by Visit 2 (exclusively home versus any hospital nights), and use of systemic corticosteroids by Visit 2.

Randomization will occur centrally using a web based randomization system linked to the electronic data capture (EDC) system. Only authorized site personnel are given access to the EDC system. Authorized site personnel will enter subject eligibility information as well as any information needed for randomization stratification. The system will provide the appropriate authorized site personnel with a randomization assignment for that subject that matches a specific treatment duration.

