9.1.14 CFFNPR Data Entry (US Sites Only)

For the hospitalization or home IV antibiotic treatment for the pulmonary exacerbation that triggers enrollment into this study, an episode must be completed in the CFFNPR.

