17.3 Informed Consent Form

Informed consent will be obtained in accordance with the Declaration of Helsinki, ICH GCP, US Code of Federal Regulations for Protection of Human Subjects (21 CFR 50.25[a,b], CFR 50.27, and CFR Part 56, Subpart A), the Health Insurance Portability and Accountability Act (HIPAA, if applicable), and local regulations.

The Investigator will prepare the informed consent form, assent (if applicable) and HIPAA authorization (if applicable) and provide the documents to the Sponsor or designee for approval prior to submission to the IRB/IEC. The consent form generated by the Investigator must be acceptable to the Sponsor and be approved by the IRB/IEC. The written consent document will embody the elements of informed consent as described in the International Conference on Harmonisation and will also comply with local regulations. The Investigator will send an IRB-approved copy of the Informed Consent Form to the Sponsor (or designee) for the study file.

A properly executed, written, informed consent will be obtained from each subject prior to entering the subject into the trial. Information should be given in both oral and written form and subjects must be given ample opportunity to inquire about details of the study. If appropriate and required by the local IRB/IEC, assent from the subject will also be obtained. If a subject is unable to sign the informed consent form and the HIPAA authorization, a legal representative may sign for the subject. A copy of the signed consent form (and assent) will be given to the subject of the subject and the original will be maintained with the subject's records.

During the course of the study, if modifications are made to the consent form that impact the subject, the subject will be re-consented as described above.

17.4 Consent for Collection and Use of CFF Registry ID Number (US Sites Only)

To facilitate future evaluation of retrospective and prospective information from all patients who screen for this study, the subject's CFF Registry ID number will be collected. The CFFNPR collects data on all CF patients who consented to participate in the CFFNPR and who are followed at CFF-accredited care centers. The registry data includes information from clinical encounters, hospitalizations courses of antibiotics, and year-end surveys. Data also include microbiology results, spirometry results, CF genotype and other information such as survival.

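### SAP 2.14: registry durations at STOP2 centres during the study include randomised courses, so a during-to-after difference can be mistaken for a change in practice

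*SAP*

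**What the plan says.** SAP 2.14 summarises registry-recorded durations of exacerbation treatment "observed at the STOP2 study centers during the conduct of this study and after the study completion". It places beside them the durations "observed at a select non-STOP2 CF centers during the same time frames". The calendar dates are still blank placeholders. The section names no pre-study period, no restriction by trial participation, no rule for choosing the comparison centres, and no test or effect measure.

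Two parts of the protocol determine what the registry will hold:

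- Protocol 9.1.14 (US sites only) says that for the course that triggered enrolment "an episode must be completed in the CFFNPR".
- Protocol 8.1 sets the length of those courses by randomisation. Early robust responders (ERR) receive "either 10 days (ERR-10) or 14 days (ERR-14) total IV antibiotic treatment duration". The remaining subjects (NERR) "will be randomized 1:1 to receive either 14 (NERR-14) or 21 (NERR-21) days total IV antibiotic treatment duration".

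Protocol 17.4 adds that, for everyone screened at US sites, the "CFF Registry ID number will be collected".

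**The concern.** The durations at STOP2 centres during the study are a mixture of courses whose length the clinician chose and courses whose length the trial assigned. The assigned courses stop when randomisation ends, and the comparison centres never have any. If clinicians at STOP2 centres change nothing, their during-study and after-study distributions can still differ, while those at the other centres stay the same. Under a heading about study impact, a reader would naturally take that pattern as evidence that the trial changed practice.

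The concurrent centres help with trends common to all centres. They do not help here, because only STOP2 centres lose assigned courses. At stake is what this one section can be used to claim.

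**Working it through.** **The plan's own figures.** SAP 2.14 gives no number, so the starting point is the number randomised. Protocol 15.7 expects about 1330 screened and 7% lost before Visit 2: 1330 × 0.93 = 1236.9, which agrees with the stated 1236.

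**Planned mix of assigned durations.** Protocol 15.7 expects ERR to NERR at 1:2, and Protocol 8.1 randomises 1:1 within each group.

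- 10 days: 1236 × 1/3 × 1/2 = 206 (1/6)
- 14 days: 206 + 412 = 618 (1/2, matching the 50% in Protocol 2.1)
- 21 days: 1236 × 2/3 × 1/2 = 412 (1/3)
- Mean: (2060 + 8652 + 8652) / 1236 = 15.67 days

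These are assigned durations. The registry holds actual ones, which spread around them through the tolerances in the Protocol Synopsis (±1 day for 10 and 14 days, ±3 for 21) and through non-adherence.

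**Volume.** 1236 over 41 months is 1236 / (41/12) = 362 courses a year, or about 6 a year at each of about 60 sites. The registry requirement covers US sites only, so 1236 is an upper figure.

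**Size of the artefact.** Let s be the trial share of registry courses at STOP2 centres during the study, t the trial share at a given duration, and u the usual-care share at that duration. With practice unchanged:

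- during = s × t + (1 − s) × u
- after = u
- after − during = s × (u − t)

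Strictly, u is the share that the enrolled patients would have had in usual care. The illustration takes it as equal to the overall usual-care share. The documents give neither s nor u, so both are assumed over a range.

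Spurious change in the 21-day share (t = 1/3), in percentage points:

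| Usual-care 21-day share | s = 5% | s = 10% | s = 20% | s = 30% |
|---|---|---|---|---|
| 0 | −1.7 | −3.3 | −6.7 | −10.0 |
| 10% | −1.2 | −2.3 | −4.7 | −7.0 |
| 20% | −0.7 | −1.3 | −2.7 | −4.0 |
| 1/3 | 0 | 0 | 0 | 0 |
| 40% | +0.3 | +0.7 | +1.3 | +2.0 |

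Other summaries for the same s (5, 10, 20, 30%):

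- **Share at exactly 14 days**, assuming 25% in usual care, s × (0.25 − 0.50): −1.25, −2.5, −5.0, −7.5 points.
- **Share above 14 days**, using the 2011 registry statement in Protocol 2 that roughly half of US patients exceed 14 days, s × (1/2 − 1/3): +0.8, +1.7, +3.3, +5.0 points. This is indicative only, since a 14-day course may run to 15 days within tolerance.
- **Mean**, assuming a usual-care mean of 14.5 days (Protocol 2 gives 14.5 as an adult median), s × (14.5 − 15.67): −0.06, −0.12, −0.23, −0.35 days.

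**Does dropping the randomised courses cure it?** Not by itself. Suppose courses of the kind enrolled make up the same share s after the study, with usual-care mean d_e, and all other courses have mean d_n. After exclusion, the during period has mean d_n. The after period has mean s × d_e + (1 − s) × d_n. The spurious shift is then s × (d_e − d_n), which is zero only if enrolled and non-enrolled patients would usually be treated for the same time. Protocol 6.3 gives reason to doubt that: it excludes recent IV antibiotics, intensive care admission, transplant and treatment for non-tuberculous mycobacteria.

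**The case against.** The case on the other side has four parts.

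- **Only description is planned.** SAP 2.14 shows distributions side by side and tests nothing. The item is not among the protocol's objectives, endpoints or analyses (Protocol 3, 5 and 15). This stands: no efficacy or safety conclusion depends on it. It does not dispose of the point, because the heading invites a causal reading.
- **The shift may be negligible or may reverse.** Protocol 2.1 describes the trial durations as in line with current practice and 14 days as the most common. This also stands. A reader might infer that STOP2 centres are bound to show a shift even if practice never changes. The documents do not support that: s and u are unknown, the 21-day artefact vanishes at one third and changes sign above it, and the shift in the mean is probably small.
- **A pre-study period is not needed if impact means uptake of results.** Protocol 2 keeps aggregate results blinded to the end, so the study period is a pre-result period, and the concurrent centres address fixed differences and shared trends. It would therefore be too strong to say that, without a pre-study window, study impact can never be separated from earlier differences. What remains is that this reference period contains assigned courses at one set of centres only.
- **Details may lie elsewhere.** SAP 1.3 refers to table and figure shells that are not in the available text. Dates or the choice of centres could be given there. The absence of a selection rule is therefore a statement about SAP 2.14 alone.

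**Conclusion.** The point holds as a limit on what SAP 2.14 can show. US index courses with assigned durations sit in the STOP2 during-study data and nowhere else in the comparison. A during-to-after difference at those centres can therefore be mistaken for changed practice, and the concurrent centres do not remove it.

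The size is s × (u − t). If trial courses are 5 to 30% of registry courses, the 21-day share moves by −1.2 to −7.0 points if usual care is 10%, by nothing if it is one third, and by +0.3 to +2.0 points if it is 40%. The mean moves by about 0.06 to 0.35 days under the assumed 14.5-day usual-care mean. These figures rest on the planned allocation, on unchanged practice, and on assumed values of s and u. The mechanism is certain; the magnitude and direction are not.

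The section merits revision because its conclusion could be wrong, but the trial's primary conclusions are unaffected.

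**What to change.** In SAP 2.14:

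1. Add a pre-study registry window, equal in length to the post-study window, for both STOP2 and non-STOP2 centres. Make the main summary the pre-to-post change at STOP2 centres beside the same change at the other centres. Neither window contains trial courses. Fill in the calendar dates.
2. If the during-study period is still shown, present randomised index courses, linked by registry ID at US sites, separately from other courses. State that the remaining courses come from a selected, non-enrolled group. Do not rely on exclusion alone as the correction.
3. Use all non-STOP2 centres, or a selection rule fixed before the data are seen.

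The cost is one wider registry extract and a little more analysis. No new data are collected, and SAP 1.3 already places registry analyses after study close-out. One limitation should be stated: the two windows lie about 42 months apart (the planned study duration), so reading the comparison as impact assumes that both sets of centres would otherwise have followed the same trend.
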